## Introduction

With an ageing population, cataract surgery has become the most common surgical procedure carried out in the developed world. Approximately 2.5 million surgeries are preformed in the USA each year and approximately 250,000 are preformed in the UK.[1] Cataract surgery is also known as phacoemulsification and involves the extraction of the natural lens from its capsular bag and implantation of an artificial intraocular lens (IOL). The evolution of IOL designs has been rapid and extensive development of new advanced IOLs has occurred in recent years; spherical monofocal IOL designs are no longer the only pseudophakic option. Multifocal IOLs (MIOLs) are popular for the surgical correction of presbyopia because their mechanism of action is independent of ciliary body function. MIOLs provide high levels of spectacle independence[2] and currently are the most reliable lens for attaining both distance and near vision. This has lead to refractive lens exchange gaining popularity as increasing numbers of presbyopic patients look for refractive solutions. Monofocal intraocular lenses are the staple of cataract surgery providing excellent distance vision, however as patients expectations and demands rise, the need for correction of intermediate and near vision has become increasingly important. MIOLs restore some visual function at different distances by creating at least two focal points within the eye, corresponding to different working distances. Several mechanisms can be employed to create the simultaneous focal points and it is important to consider an MIOL's method of action as each lens has its own unique optical properties. The design of the MIOL affects the light distribution, the number of focal points, the distance of their separation, and ultimately the quality of the images. MIOLs can be divided into diffractive and refractive designs. Refractive designs can be subdivided into concentric and sectorial, while diffractive designs can be categorised as fully diffractive or partially diffractive.

Intermediate visual function has posed a problem with MIOL implantation. A drop in acuity in the intermediate range has been reported with bifocal multifocal lenses. [3-5] Good intermediate vision is a requirement for certain individuals for occupational or recreational purposes and a sub-optimal acuity in the intermediate range can have a negative influence on the individual's quality of life[6] To this end recent MIOLs have been designed to improve intermediate vision by the use of a

lower add. These lenses provided good distance and near acuity as well as acceptable intermediate vision.[7-10]

With intermediate and near vision being essential in most individual's daily routine, it is clear that a solution is required and an IOL that can provide good vision at intermediate and near, without detriment to distance vision is needed. Visual acuity alone is not an adequate measure of success with MIOLs. All MIOLs create two or more simultaneous focal points within the eye. Therefore, at any one time at least one focal point will not be convergent on the retina. This defocused image causes a reduction in contrast and a distinctive photopic phenomenon known as Dysphotopsia.[2,12] This phenomenon, is one of the most common complaints with multifocal implantation and needs to be investigated to fully understand how the optical properties of an MIOL affect this photopic phenomenon.

### **Aims:**

This study aims to evaluate the visual function and patient satisfaction of patients who have been implanted with the BiFlex M Multifocal IOL (Medicontur) and to compare the results with patients implanted with the BiFlex 1.8 monofocal IOL.

### **Methodology:**

This prospective randomised control study will evaluate 100 patients (200 eyes) having undergone bilateral implantation with either the multifocal or monofocal IOLs for either cataract or clear lens extraction surgery.

Preoperatively all patients have comprehensive ophthalmological examination, including detailed history, refraction, dilated fundus examination, tonometry and slit lamp examination to exclude pre-existing conditions which may limit the refractive outcome. IOL power calculations will be performed using a Haag Streit LS900 Lenstar biometer. All patients will be adequately informed and sign a consent form.

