### **Inclusion Criteria:**

Age 50-75 years, bilateral IOL implantation.

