### **Exclusion Criteria:**

Amblyopia, post-op corneal astigmatism of  $\geq 1.50\text{D}$ , visual axis eccentricity of greater than 0.7mm, macular pathology, glaucoma, retinal disease, corneal disease, abnormal iris, pupil deformation and any previous corneal or intraocular surgery.

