### **Methods**

Each subject will be evaluated at three visits following IOL implantation; visit 1 (1 month), Visit 2 (3-6 months) and visit 3 (12-18 months).

At each visit the following non-invasive visual function tests will be conducted: Monocular and binocular Unaided (UCVA) and Best Corrected Visual Acuity (BCVA) will be measured at 6 meters in LogMAR units using a calibrated computerised test chart.

Subjective and objective refraction will be used to determine if there is any residual refractive error.

Defocus curve profiles (visual acuity over imposed defocus) will be measured for each patient over a defocus range of +1.50D to -5.00D in 0.50D steps. The presentation of the letters and lenses will be randomised.

Contrast sensitivity will be evaluated monocularly under photopic and mesopic conditions using the Pelli-Robson Contrast Sensitivity Chart and CSV-1000.

Best distance corrected near and intermediate reading performance will be evaluated using the Radner Reading Charts and LogMAR charts and reading speed will be assessed in photopic conditions

Uncorrected and best distance corrected near acuity will be measured at 40cm

Uncorrected and best distance corrected intermediate acuity will be measured at 70cm.

The subject will be shown the Glare Simulator (Carl Zeiss Meditec) in order to assess the type of dysphotopsia present at each visit

A Halometer will be used to determine the size of the dysphotopsia

In order to assess the ocular biometry and record features of the IOL, at each visit the following imaging tests will be conducted following instillation of Tropicamide 1% to dilate the pupil:

- The Lenstar (Haagstreich) will be used to determine the post-operative axial position of the IOL following implantation.
- The A digital slit lamp camera will be used to image the IOL. This image will be used to determine if any decentration is present and if posterior capsular opacification is present using the EPCO 2000 software programme.

At each visit the following subjective assessment tests will be given to the patient to complete:

- The Visual satisfaction questionnaire will be used to determine the patient's overall satisfaction with their vision
- Near Assessment Visual Questionnaire (NAVQ) will be used to assess the patients satisfaction with their near and intermediate vision[14]

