#### **Statistical Analysis:**

Normal distribution will be determined through examining histogram plots and with the Kolmogorov-Smirnov test. For analysis of the defocus curves the data will first be transformed into the defocus area metric[15] and the Radner reading chart data will also be converted according to the reading performance index.[16] Following this the means from each group will be assessed using two-way repeated measures ANOVA and a Pearson's coefficient will be used to look for correlations within the data. The results from the visual satisfaction questionnaire and NAVQ will be converted into Log RASCH units to provide a linear scale.

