#### **Sample Size**

Using GPower 3 a sample size of 50 subjects (100 eyes) per group was calculated for this study, therefore a total of 100 subjects will be recruited for the study.

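### Optional efficiency gain: cataract and clear-lens patients are pooled and the lens comparison names no covariate for surgical indication

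*Combined protocol and SAP*

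**What the plan says.** - **Population.** The Methodology section describes a randomised study of 100 patients receiving one of two lenses in both eyes "for either cataract or clear lens extraction surgery". The inclusion criteria, "Age 50-75 years, bilateral IOL implantation", do not restrict by indication.
- **Analysis.** After the defocus and reading data are transformed, "the means from each group will be assessed using two-way repeated measures ANOVA". The two factors are not named; lens group and visit is the natural reading, given three visits. No covariate, subgroup or stratified analysis is mentioned.
- **Randomisation.** The study is called randomised, but no method or stratification factor is given.
- **Sample size.** "a sample size of 50 subjects (100 eyes) per group was calculated for this study", with no endpoint, effect size, SD, significance level or power.
- **Outcomes.** The aim is "to evaluate the visual function and patient satisfaction of patients" and to compare the two lenses. Satisfaction is measured at every visit by a questionnaire on "overall satisfaction with their vision" and by the NAVQ for near and intermediate vision.

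**The concern.** Patients having a cataract removed and patients exchanging a clear lens may come with different expectations. The Introduction links the growth of lens exchange to the fact that "increasing numbers of presbyopic patients look for refractive solutions". If scores differ by indication, an analysis that ignores it leaves the difference in the error term. An arm that happens to receive more clear-lens patients then carries that difference into the lens contrast.

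Satisfaction is one of the two stated aims, and the two questionnaires are where a link with indication is most plausible. The argument is weaker for halometry and defocus curves. It applies only to the between-group comparison, because an indication effect that is constant over visits cancels out of a group-by-visit test. At stake are some precision and protection against a chance imbalance.

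**Working it through.** **The plan's own figure.** The 50 per group cannot be reproduced, because the Sample Size section gives no inputs. Working backwards with a two-sided 5% t test (98 df), 80% power needs a noncentrality of 2.829. Noncentrality is d × √(50/2) = 5d, so d = 2.829/5 = 0.566 SD. This serves only as a baseline.

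**Inputs.** Given: 100 patients, 50 per arm. Assumed, because not given: two-sided 5%, 80% unadjusted power, one score per patient, simple 1:1 allocation, clear-lens share p of 5% to 50%, and an indication effect D (in within-indication SDs) equal in both arms.

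**Chance imbalance.** With K clear-lens patients, the number k in one arm is hypergeometric and the gap is |2k − K|/50.
- A gap of 10 points or more has probability 2·C(50,5)/C(100,5) = 0.056 at K = 5, 0.09 at K = 10, 0.28 at K = 30, 0.32 at K = 50 and at most 0.42 (K = 49).
- The values jump between odd and even K. The lowest from K = 5 to 50 is 2·C(50,6)/C(100,6) = 0.027, at K = 6.
- A gap of 20 points or more has probability 0.001 at K = 10 and 0.07 at K = 50.
- With D = 0.5, a 10-point gap shifts the lens difference by 0.10 × 0.5 = 0.05 SD. At p = 0.5 the SE is √(2 × 1.0625/50) = 0.206 SD, so the shift is about a quarter of an SE.

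**Precision.** The unadjusted variance per patient is v = 1 + p(1 − p)D². Adjusting removes the second term but inflates the variance for chance correlation between covariate and arm, on average by 48.5/48 = 1 + 1/96. The net gain in patients is v/(1 + 1/96) − 1. Break-even is at D = √[(1/96)/(p(1 − p))]. Power uses noncentrality 2.829 × √[v/(1 + 1/96)] on 97 df. For example, at p = 0.5 and D = 0.5, v = 1.0625, the ratio is 1.0515, the noncentrality is 2.901 and power is 81.9%.

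| Clear-lens share | Break-even D | D = 0 | D = 0.5 | D = 0.8 |
|---|---|---|---|---|
| 5% | 0.47 | 79.6% (−1.0%) | 80.0% (+0.1%) | 80.8% (+2.0%) |
| 10% | 0.34 | 79.6% (−1.0%) | 80.5% (+1.2%) | 81.8% (+4.7%) |
| 30% | 0.22 | 79.6% (−1.0%) | 81.6% (+4.2%) | 84.3% (+12.3%) |
| 50% | 0.20 | 79.6% (−1.0%) | 81.9% (+5.2%) | 85.1% (+14.8%) |

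Entries are adjusted power, with the net gain in patients in brackets.

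**Source of the cost.** Losing one degree of freedom alone leaves power at 79.99%. Nearly all of the fall to 79.6% comes from the 1/96 term.

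**If the effect differs by lens** (p = 0.5). With 0.5 SD in one arm and 0 in the other, the total variance is 1 + 0.25 × (0.25 + 0)/2 = 1.03125. After an additive covariate it is 1 + 0.25 × 0.25² = 1.015625. The net is 1.03125/1.015625/(1 + 1/96) − 1 = +0.5%. With opposite effects of 0.5 SD, both variances are 1.0625 and the net is −1.0%.

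**Stratifying without adjusting.** Type I error is about 2[1 − Φ(1.96√v)]. At D = 0.5 this is 4.9% (p = 0.05) to 4.3% (p = 0.5); at D = 1.0 it is 4.5% to 2.8%. The test becomes conservative.

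**The case against.** **The benefit is unproven and may be negligible.** No section says how many patients have clear lenses or that scores differ by indication within a lens arm. The Introduction presents cataract surgery as the high-volume procedure, so a low clear-lens share is quite consistent with the text. At such shares the gain at 0.5 SD is about 1% of patients or less. This stands, and is why the range runs down to 5%.

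**The plausible mechanism may be an interaction.** A wish for spectacle independence could affect how a patient reacts to a multifocal as against a monofocal lens. An additive covariate recovers little or nothing in that case. This also stands, so the common effect must be stated as an assumption.

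**The remedy could be spread too widely.** Where indication is not prognostic, the covariate costs a little. This supports giving priority to the two questionnaires.

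**Stronger readings that the documents do not support.** A reader might infer that pooling biases the lens comparison or inflates its type I error. Under proper randomisation it does neither: simulated type I error for the unadjusted, unstratified test was 4.8% to 5.1%. A reader might also infer that age and surgeon need adjustment. Age is limited to 50 to 75, ocular disease and "any previous corneal or intraocular surgery" are excluded, and both surgeons are described as experienced and use one standard technique. If surgeon and age add nothing, a three-covariate model breaks even only at 0.36 to 0.39 SD (30% to 50% clear lens), against 0.20 to 0.22 SD for indication alone.

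The objections do not remove the asymmetry: the worst case costs about 0.4 power points, and the gain is several times that if indication matters and the sample is mixed.

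**Conclusion.** The point holds as an optional, low-cost improvement in efficiency. The plan creates a known heterogeneity and, as written, handles it in neither allocation nor analysis. The planned comparison remains valid.

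The gain is small at 0.5 SD (at most 1.9 power points) and becomes material only with an effect near 0.8 SD or more and a well-mixed sample (up to 5.1 points at 0.8 SD). Below break-even it is a slight loss. All sizes rest on assumed power, case mix and a common indication effect, and the gain is smaller or nil if the effect differs between lenses. The case is best supported for the two questionnaires.

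**What to change.** Add to the Statistical Analysis section that the lens-group comparison includes indication as one fixed between-subject covariate, at least for the visual satisfaction questionnaire and the NAVQ. Define it in writing: cataract or clear lens, as recorded preoperatively, one category per patient, with a rule for eyes that differ (for example, cataract if either eye has cataract). Settle this before outcome data are seen, so that adjustment is not prompted by an observed imbalance.

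If recruitment has not started, also stratify randomisation by indication in permuted blocks and keep it in the model. Add surgeon only if it is used to stratify, and do not add age by default.

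The cost is one analysis sentence, one definition and, where applicable, one sentence on randomisation. No new test is needed, since history and slit lamp examination are already part of the preoperative work-up, and the sample size does not change. The statistical downside if indication is not prognostic is the roughly 1% of patients shown above. It is close to nil (80.0% power) if randomisation is also stratified.

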### **Inclusion Criteria:**

Age 50-75 years, bilateral IOL implantation.

### **Exclusion Criteria:**

Amblyopia, post-op corneal astigmatism of  $\geq 1.50\text{D}$ , visual axis eccentricity of greater than 0.7mm, macular pathology, glaucoma, retinal disease, corneal disease, abnormal iris, pupil deformation and any previous corneal or intraocular surgery.

### **Surgical Technique:**

All surgeries will be performed by one of two experienced ophthalmic surgeons using a standard, sutureless, microincision, phacoemulsification technique under topical anaesthesia. Routine post-op drug regime will be followed.

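### Two surgeons operate, but the protocol does not state that lens allocation is balanced within surgeon, and the group comparison names no surgeon term

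*Combined protocol and SAP*

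**What the plan says.** All statements are in the combined protocol and SAP.

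- **Surgical Technique:** "All surgeries will be performed by one of two experienced ophthalmic surgeons". One standard technique is specified for both. The split of cases between the surgeons, and how a patient comes to one or the other, are not given.
- **Methodology:** "This prospective randomised control study will evaluate 100 patients (200 eyes) having undergone bilateral implantation". The study is called randomised, but no sequence, blocking, stratification or concealment is described.
- **Sample Size:** "Using GPower 3 a sample size of 50 subjects (100 eyes) per group was calculated for this study", which gives equal arms of 50 patients.
- **Methods:** outcomes that plausibly depend on the operator are recorded at each visit. On refraction: "Subjective and objective refraction will be used to determine if there is any residual refractive error". On the slit lamp image: "This image will be used to determine if any decentration is present and if posterior capsular opacification is present". Uncorrected acuity and the axial position of the lens are also measured.
- **Statistical Analysis:** "Following this the means from each group will be assessed using two-way repeated measures ANOVA". The two factors of this ANOVA are not named, and surgeon is not mentioned.

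**The concern.** Residual refraction (and through it uncorrected acuity), centration, axial position and capsule opacification can all vary with who operates. If one surgeon happens to implant more of the multifocal lenses, part of any difference between surgeons enters the observed lens difference, and a comparison of arm means without surgeon neither shows this nor corrects it. With only two surgeons, balance within surgeon is easy to secure by design, and the protocol does not say that it will be. At stake are the credibility of the lens estimate in the trial actually obtained and some power.

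**Working it through.** **Inputs from the document.** Two surgeons; 50 patients per lens; 100 in total.

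**Assumed, because the document gives none.** 50 patients per surgeon; one value per patient; two-sided alpha 0.05; within-surgeon SD of 1; surgeon effect g of 0.3, 0.5 or 1.0 SD.

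**The plan's own figure.** The 50 per group cannot be reproduced, because no alpha, power, effect size or SD is stated. At 80% power, 50 per group corresponds to a detectable difference of √(2/50) × (1.960 + 0.842) = 0.56 SD by the normal approximation. With the t distribution, a lens effect of 0.566 SD gives power 0.80, so I use 0.566 below.

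**1. Chance imbalance.** Let x be the number of one surgeon's 50 patients who receive the multifocal lens. Under simple 1:1 allocation x is hypergeometric (100, 50, 50), and the arm difference in that surgeon's share is (2x − 50)/50.

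- Var(x) = 50 × 0.5 × 0.5 × 50/99 = 6.313, so the SD of x is 2.513.
- SD of the share difference = 2 × 2.513/50 = 0.1005, or 10 percentage points.
- P(gap of 10 points or more) = 0.32; 20 or more = 0.071; 30 or more = 0.003.
- If the surgeons split cases 70:30, P(20 points or more) = 0.049.

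**2. Shift in the lens difference.** Shift = share difference × g. At 20 points:

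- g = 0.3: 0.20 × 0.3 = 0.06 SD.
- g = 0.5: 0.20 × 0.5 = 0.10 SD.

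The standard error of the lens difference is √(2/50) = 0.20 SD, so these shifts are 0.3 and 0.5 standard errors. Given a gap of exactly 20 points, the noncentral t (98 df) puts the false-positive rate at 0.060 and 0.079. These rates are conditional on the imbalance.

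**3. Overall false-positive rate.** Over all randomisations, with no surgeon term, simulation of 40,000 trials gave 0.050 (g = 0.3), 0.049 (g = 0.5) and 0.050 (g = 1.0). With a surgeon term it gave 0.051, 0.049 and 0.050. Both are nominal.

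**4. Power at a lens effect of 0.566 SD.** Without surgeon in the model, its variance stays in the error: the SD becomes √(1 + 0.25g²). With surgeon in the model and balanced allocation, the SD is 1 and the noncentrality is 0.566/0.20 = 2.83 on 97 df.

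| g | SD without surgeon | Standard error | Noncentrality | Power without | Power with |
|---|---|---|---|---|---|
| 0.3 | 1.011 | 0.2022 | 2.80 | 0.79 | 0.80 |
| 0.5 | 1.031 | 0.2062 | 2.75 | 0.78 | 0.80 |
| 1.0 | 1.118 | 0.2236 | 2.53 | 0.71 | 0.80 |

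The simulation agrees: 0.790, 0.779 and 0.705 without the term. With the term but without stratified allocation it gave 0.794, 0.799 and 0.795. The sample size need not change.

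**The case against.** The strongest reply is that randomisation already deals with surgeon. It balances surgeon in expectation, and the standard error of an unadjusted comparison allows for chance imbalance, whatever the number of surgeons. That stands, and step 3 confirms it.

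A reader might infer more: that with two operators the imbalance systematically distorts the lens effect, or that lens choice follows surgeon habit. The documents do not support either. Splits of 80/20 against 20/80 would be a 60-point gap, which has probability of about 2 in 10⁹ under the allocation in step 1, so it would require lens to be tied to surgeon. No section says that it is; the study is described as randomised. Nor can one say that allocation is unbalanced within surgeon: no allocation method is given, so the text shows neither balance nor imbalance. That missing method is the larger gap, and this point is one specific part of it. A general description of randomisation would not by itself bring in stratification by surgeon or a surgeon term.

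Three further points limit the reach of the concern:

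- Much of the near, intermediate and reading assessment is done with best distance correction, which narrows the route through residual refraction.
- Statistical Analysis names no specific analysis of decentration, axial position or capsule opacification.
- A common technique, and the exclusion for post-operative corneal astigmatism, should reduce differences between surgeons.

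These make a large surgeon effect less likely for some outcomes but do not exclude one. Uncorrected acuity at distance, intermediate and near is still measured.

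**Conclusion.** The point holds as a matter of precision and of protection against an unlucky allocation. It is not a demonstrated bias. Given the stated randomisation, the overall false-positive rate is about 5% with or without surgeon in the model. The 6% to 8% rates apply only to a trial that has a 20-point gap, and gaps of that size or more arise in about 7% of trials. The shift is then 0.06 to 0.10 SD, against a standard error of 0.20 SD. The power lost by omitting surgeon is 1 to 2 percentage points for surgeon effects of 0.3 to 0.5 SD, and 9 points at 1.0 SD. All of this rests on an assumed surgeon effect, an even case split, an analysis by patient and a lens effect of 0.566 SD. The change is worth making because it is nearly free.

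**What to change.** - **Methodology and Surgical Technique:** state that patients are randomised to lens within operating surgeon, in permuted blocks of randomly varying size, from a concealed list, so that each surgeon implants about equal numbers of both lenses.
- **Statistical Analysis:** add surgeon as a between-patient factor in the group comparison. The two changes belong together: if allocation is stratified but surgeon is left out of the model, the surgeon variance stays in the error term and the test becomes conservative.

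**Cost.** Two allocation lists instead of one, one degree of freedom, and the operating surgeon must be known before allocation. Blocks within surgeon make the next allocation somewhat more predictable, since the surgeon sees which lens is implanted; varying block sizes and concealment limit this. No extra patients are needed.
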